
Aim II: For this aim, the endpoint is change in myocardial ECV assessed by myocardial T1 mapping on cardiac MRI. Secondary endpoints will include the following: change in plasma IL-6, MCP-1, sCD163, sCD14 and serum hsCRP, galectin-3, cardiotrophin 1, lipocalin, PINP, PIIINP, BNP. Statistical algorithms as detailed in Aim I will be applied to

Mineralocorticoid Receptor Antagonism for Cardiovascular Health in HIV The MIRACLE HIV Study

these specific endpoints. Similar to Aim I, changes in ECV and inflammatory/fibrosis biomarkers over 12 mos comparing eplerenone vs. placebo will be assessed using ITT and longitudinal linear effects modeling with imputation and sensitivity analyses. By regression techniques and covariate analyses, we will also assess whether improvements in ECV from MR blockade will relate to improvements in diastolic strain.

Sample Size Determination: Thiara et al. show mean \pm SD ECV 0.28 ± 0.04 vs. 0.26 ± 0.03 in HIV vs. non-HIV using cardiac MRI.³⁰ To estimate the SD of change in ECV, we assumed an intrasubject longitudinal correlation over time $r=0.7$ among the HIV group, which results in a conservative SD estimate of 0.03. Based on this SD, the proposed study, with a revised sample size of 80 subjects and therefore 68 evaluable subjects considering a 15% attrition rate, will attain 85% power at a two sided α of 0.05 to detect a difference of at least 0.02 in longitudinal means of ECV. Thus our study is well powered to find a significant difference between arms that is clinically relevant, as each 0.03 increase in ECV raises the risk for mortality or CV morbidity by 50%.²³ For biomarkers, we have 85% power at a two-sided 0.05 α level to show a change of at least 0.74 SD comparing eplerenone vs. placebo.

Aim III: For this aim, the endpoint is change in noncalcified plaque volume assessed by coronary CTA. Secondary endpoints will include: change in high risk plaque morphology (numbers of low attenuation and positively remodeled plaque) by coronary CTA.

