Statistical algorithms as detailed in Aim I will be applied to these specific endpoints. Moreover, the relationship between baseline CFR and non-calcified plaque volume will be assessed. Lastly, we will also determine whether longitudinal changes in coronary plaque are associated with changes in biomarkers of inflammation and immune activation to understand the potential relationship of these inflammatory indices as markers of improved indices of the coronary vasculature in response to MR blockade in the HIV. **Sample Size Determination:** In our prior studies assessing plaque in HIV, the median [IQR] change of noncalcified plaque volume over 12 mos was $6.7[-6.5, 29.8]$ mm 3 .¹³ We assumed a conservative SD of 18mm 3 taking the mean of the IQR. This study enrolling 80 subjects with 68 evaluable subjects will attain 85% power at a two sided α of 0.05 to detect a difference in noncalcified plaque volume of 13.3mm 3 between eplerenone vs. placebo, a clinically relevant change. For biomarkers, this study has 85% power at a two-sided 0.05 α level to show a change of at least 0.74 SD after treatment with eplerenone vs. placebo.

Aim IV: For this aim, the endpoint is change in MCP-1 between the low sodium and liberal sodium diets. Secondary endpoints will include: change in hsCRP, pentraxin3, IL6, Lp-PLA $_2$, sCD14, sCD163. We will test the change in biomarkers between the RAAS activated (sodium restricted) and RAAS suppressed states (sodium loaded) using the paired Student's t-test for normally distributed variables or Wilcoxon signed-rank test for non-normally distributed variables. We will apply Pearson's correlation for variables that are normally distributed and Spearman's correlation for variables that are non-normally distributed to determine whether there is a significant correlation between aldosterone during the RAAS activated state and TBR. Covariates considered for inclusion in modeling include variables that may affect vascular dysfunction, inflammation, and plaque (age, race, sex, BP, tobacco/illicit drug use, family history of CVD, lipids, glucose), and HIV parameters (viral load, CD4, duration of HIV and ART use). This will permit us to assess relevant factors that may mediate the effect of aldosterone on inflammation in HIV and interactions between HIV and traditional risk factors contributing to inflammation. **Sample Size Determination:** Preliminary data in HIV presented in this

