MIneralocorticoid Receptor Antagonism for CardiovascuLar hEalth in HIV The MIRACLE HIV Study

grant demonstrate a mean change in MCP-1 of 44.0 ± 41.8 pg/mL between a low sodium and ad lib sodium diet. Based on this SD, the proposed study, with a sample size of 42 subjects, and therefore 36 evaluable subjects considering a 15% attrition rate, will attain 85% power at a two sided α of 0.05 to detect a difference of at least 44.0 pg/mL in mean MCP-1 between the formally tested RAAS activated (sodium restricted) and RAAS suppressed (sodium loaded) states. For other biomarkers, we have 85% power at a two-sided 0.05 α level to show a change of at least 0.95 SD between RAAS activated and suppressed states.

Aim V: For this aim, the endpoint is change in TBR assessed by cardiac ^{18}F -FDG-PET/CT. Secondary endpoints include: change in hsCRP, pentraxin3, IL6, Lp-PLA2, MCP-1, sCD14, sCD163. Statistical algorithms as detailed in Aim I will be applied to these specific endpoints. Similar to Aim I, changes in TBR and inflammatory biomarkers over 12 mos comparing eplerenone vs. placebo will be assessed using ITT and longitudinal linear effects modeling with imputation and sensitivity analyses. We will also determine whether longitudinal changes in arterial inflammation are associated with changes in biomarkers of inflammation and immune activation to understand the potential relationship of these inflammatory indices as markers of improved indices of the coronary vasculature in response to MR blockade in the HIV. **Sample Size**

Determination: In our prior studies assessing arterial inflammation on ^{18}F -FDG PET, the mean \pm SD (95% CI) TBR at baseline among HIV subjects was 2.23 ± 0.45 (2.07, 2.40)mm 3 .⁷⁴ In order to estimate the SD of change in TBR, we assumed the intrasubject longitudinal correlation over time $r=0.75$, which results in a conservative SD estimate of 0.34. This study enrolling 42 subjects with 36 evaluable subjects will attain 85% power at a two sided α of 0.05 to detect a difference in mean TBR changes of 0.32 between eplerenone vs. placebo, a clinically relevant difference in the changes as our preliminary data show that non-HIV subjects have a mean TBR 1.89. For biomarkers, this study has 85% power at a two-sided 0.05 α level to show a mean change of at least 0.95 SD after treatment with eplerenone vs. placebo.

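### Optional substudy (Aims IV and V): the 85% power figures do not match the stated 36 evaluable subjects. Aim V's have 78–79% power, and Aim IV's 0.95 SD is not a paired-test figure.

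*Combined protocol and SAP*

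**What the plan says.** All references are to section VI, Biostatistical Analysis.

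- **Aim V, Sample Size Determination:** "This study enrolling 42 subjects with 36 evaluable subjects will attain 85% power", two-sided at 0.05, "to detect a difference in mean TBR changes of 0.32 between eplerenone vs. placebo". The SD of the change is built from a baseline SD of 0.45 and a within-subject correlation of 0.75, "which results in a conservative SD estimate of 0.34". For biomarkers the claim is 85% power "to show a mean change of at least 0.95 SD after treatment with eplerenone vs. placebo". The analysis follows Aim I, which is a two-sample t-test or rank sum test on the change.
- **Aim IV:** the two dietary states are compared within subject, "using the paired Student's t-test for normally distributed variables" (signed-rank test otherwise). With 36 evaluable, the text claims 85% power for 44.0 pg/mL in MCP-1 (SD 41.8) and, for other biomarkers, "to show a change of at least 0.95 SD between RAAS activated and suppressed states".
- **Main study, for comparison:** "This study enrolling 80 subjects with 68 evaluable subjects will attain 85% power" under Aim III. Under Aim II the biomarker statement is "to show a change of at least 0.74 SD comparing eplerenone vs. placebo".

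**The concern.** The same 0.95 SD is printed for a two-arm comparison (Aim V) and a within-subject comparison (Aim IV). With the same 36 subjects these designs cannot have the same detectable effect, so at least one figure is wrong. In addition, 0.95 SD looks too small for 18 per arm at 85% power.

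Aim V calls 0.32 TBR clinically relevant and claims 85% power for it. If power is really about 78%, the chance of missing that difference is about 22% rather than 15%, and a null TBR or biomarker result would be read with more confidence than the design supports. Aim IV carries the opposite risk: the paired design is presented as almost half as sensitive as it is.

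**Working it through.** **Inputs.** Aim V: 42 enrolled, 36 evaluable (42 × 0.85 = 35.7), 85% power, two-sided 0.05, SD of change 0.34, baseline SD 0.45, r=0.75. Aim IV: 36 pairs, SD of change 41.8 pg/mL. Allocation is 1:1 (section IV), so 18 per arm is assumed for 36 evaluable. Power is from the noncentral t distribution. For two arms of n the noncentrality is d·√(n/2); for n pairs it is d·√n.

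**1. Which convention does the protocol use?** With 68 evaluable, 34 per arm, 85% power is reached at d = 0.7375.

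| Main-study figure | Printed | 34 per arm (evaluable) | 40 per arm (enrolled) |
|---|---|---|---|
| Biomarkers, SD units | 0.74 | 0.738 | 0.678 |
| CFR, SD 0.93 | 0.69 | 0.7375 × 0.93 = 0.686 | 0.678 × 0.93 = 0.631 |
| Noncalcified plaque, SD 18 mm³ | 13.3 | 0.7375 × 18 = 13.28 | 0.678 × 18 = 12.2 |

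The main study therefore uses evaluable numbers and the t distribution.

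**2. Aim V by the same method.**

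| Quantity | Printed | 18 per arm (36 evaluable) | 21 per arm (42 enrolled) |
|---|---|---|---|
| Detectable at 85%, SD units | 0.95 | 1.028 | 0.948 |
| Detectable at 85%, TBR at SD 0.34 | 0.32 | 1.028 × 0.34 = 0.350 | 0.948 × 0.34 = 0.322 |
| Power at 0.95 SD | 85% | 79.1% | 85.2% |
| Power at 0.32/0.34 = 0.941 SD | 85% | 78.3% | 84.5% |

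A normal approximation at 18 per arm gives 0.999 SD and 0.999 × 0.34 = 0.340, with power of 81.3% at 0.95 SD and 80.6% at 0.32. It does not reproduce the printed figures with the printed SD.

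**3. The SD of change in TBR.** SD of change = SD·√(2(1 − r)) = 0.45 × √(2 × 0.25) = 0.318. Working back from 0.34, r = 1 − 0.34²/(2 × 0.45²) = 0.715, not 0.75. With 0.318 and 18 per arm, the detectable difference is 1.028 × 0.318 = 0.327 and power at 0.32 is 83.4%. The 0.95 SD statement is in SD units, so it does not depend on this choice.

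**4. Numbers needed to keep Aim V's printed figures at 85%.**
- 0.95 SD: 21 per arm (85.2%), so 42 evaluable; 42/0.85 = 49.4, or 50 enrolled.
- 0.32 at SD 0.34: 21 per arm gives 84.5% and 22 gives 86.2%, so 44 evaluable; 44/0.85 = 51.8, or 52 enrolled.

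**5. Aim IV, paired test with 36 pairs.**
- Detectable change at 85% power: 0.514 SD of the within-subject change. For MCP-1 this is 0.514 × 41.8 = 21.5 pg/mL.
- Power at 0.95 SD is 99.98%; 12 pairs would give 84.9% and 13 pairs 88.1%.
- Power at 44.0/41.8 = 1.05 SD is above 99.9%.
- If SD means the SD of the level, the detectable shift is 0.514 × √(2(1 − ρ)). That is 0.73 at ρ = 0 and smaller for any positive ρ. Reaching 0.95 would need ρ = −0.71.

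The printed 0.95 SD is the same as Aim V's two-arm figure, although Aim IV has no arms.

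**The case against.** The strongest counter-argument concerns TBR. With the unrounded SD of 0.318, a normal approximation at 18 per arm gives 0.999 × 0.318 = 0.318, which rounds to the printed 0.32, and power at 0.32 is 85.5%. On that route the TBR figure would be right for 36 evaluable. It is a fair point, and it means the TBR shortfall is conditional on the SD. But it departs from the 0.34 that the paragraph prints and from the t-based method that the main-study figures follow (a normal approximation there gives 0.727 SD, against the printed 0.74). It also cannot rescue the 0.95 SD statement.

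On the SD itself, the text calls 0.34 conservative, and 0.34 is indeed larger than 0.318. It may simply have been rounded up, in which case a clarifying phrase is enough.

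On Aim IV, the statements are not false: 36 pairs exceed 85% power at both 0.95 SD and 44.0 pg/mL, and it is legitimate to power on an effect seen in preliminary data. This part stands as an understatement of sensitivity, not a shortfall. Even so, 0.95 SD is not the smallest effect detectable at 85%, which is what the matching main-study statements give.

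Finally, both aims are optional and the fix changes no conduct. That limits the weight of the point; it does not make the printed power right.

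**Conclusion.** The point holds. At the stated 36 evaluable subjects, Aim V's 0.95 SD has 79% power and its 0.32 TBR has 78% at the printed SD of 0.34. The values that match 85% are 1.03 SD and 0.35 TBR. With the derived SD of 0.318, power at 0.32 is 83% and the 85% value is 0.327. The printed figures are consistent with using the 42 enrolled, but the document does not state the cause. Aim IV's 0.95 SD overstates the paired detectable change almost two-fold; the paired figure is 0.51 SD.

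These results assume an even 18/18 split, the t-test and two-sided 0.05. Randomisation is not stratified by substudy participation, so the split may be uneven, which would lower Aim V's power: 17/19 needs 1.030 SD, and 12/24 gives 74% and 73% power for 0.95 SD and 0.32.

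The consequence is limited. The Aim I and Aim III figures reproduce, and no enrolment target, analysis or decision rule is affected. The stated power should still be corrected.

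**What to change.** Keep enrolment at 42 and restate the Sample Size Determination paragraphs of Aims IV and V.

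- **Aim V:** at 36 evaluable and SD 0.34, state 85% power for a TBR difference of 0.35 (or 78% power for 0.32), and 85% power for 1.03 SD in biomarkers.
- **Aim V, SD:** reconcile 0.34 with r=0.75, either by saying that 0.34 was rounded up from 0.318 or by giving the r actually used. If 0.318 is adopted, the TBR figures become 0.327 at 85% power, or 83% power at 0.32.
- **Aim IV:** state that 36 pairs give 85% power for 0.51 SD of the within-subject change, which is 21.5 pg/mL for MCP-1 at SD 41.8.

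The cost is the wording of two paragraphs, with no change to enrolment, procedures or analysis.

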- b) MR blockade will improve markers of inflammation and immune activation.
- c) Reduced myocardial fibrosis and inflammation resulting from MR blockade will relate to improvements in diastolic dysfunction evaluated through diastolic strain by tagged myocardial imaging on cardiac MRI.

❖ **Specific Aim III: The effect of MR blockade on coronary plaque.**

We hypothesize:

- a) MR blockade will result in plaque regression and reduced high risk plaque Morphology on coronary computed tomography angiography (CTA).
- b) Baseline CFR will relate to coronary plaque features in HIV patients with subclinical atherosclerosis.
- c) Improvements in coronary plaque with MR blockade will relate to improvements in CFR and inflammation.

**Mineralocorticoid Receptor Antagonism for Cardiovascular Health in HIV
The MIRACLE HIV Study**

Optional Substudy--

❖ **Specific Aim IV: The effect of RAAS activation on systemic inflammation and specific indices of arterial inflammation.**

We hypothesize:

- a) Markers of systemic and arterial inflammation will be increased during the RAAS activated state (under carefully controlled conditions of sodium restriction) when compared to the RAAS suppressed state (under carefully controlled conditions of sodium loading).
- b) Higher serum aldosterone levels during the RAAS activated state (under carefully controlled conditions of sodium restriction) will be related to greater in situ arterial inflammation measured by aortic TBR using cardiac 2-deoxy-2-18F-Fluorodeoxyglucose Positron Emission Tomography/Computed Tomography (¹⁸F-FDG-PET/CT).

❖ **Specific Aim V: The effect of MR blockade on arterial inflammation.**

We hypothesize:

- a) Treatment with MR blockade for 12 months will reduce in situ arterial inflammation measured by aortic TBR using cardiac ¹⁸F-FDG-PET/CT.
- b) Treatment with MR will reduce markers of systemic and vascular inflammation.
- c) Changes in aortic TBR will be related to changes in markers of arterial inflammation.

Optional Study for those who do not qualify following both screen visits—

❖ **Specific Aim VI: The degree of inflammation and cardiometabolic disease among those with/without visceral fat and those with/without coronary plaque**

We hypothesize:

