- a) Worsening markers of inflammation and heart disease across the spectrum stratified by presence and absence of excess VAT and presence and absence of coronary plaque (i.e. increased worsening across the following groups: low VAT/absence of plaque, low VAT/presence of plaque, high VAT/absence of plaque, high VAT/presence of plaque).

III. Subject Selection

Inclusion/Exclusion:

Inclusion Criteria: Up to 160 HIV male and female subjects will be consented to achieve the number of evaluable subjects. 42 subjects will be consented for the optional study.

Subjects will be included for:

- 1) Ages 40-65 years
- 2) Antiretroviral use (ART) >12 months and viral load <100 copies/mL
- 3) VAT > 110cm²

Exclusion Criteria:

- 1) Antihypertensive use including, ACE Inhibitor, ARB, MR blockade, diuretic, potassium (K) supplementation; or BP > 140/90 mmHg. Stable use (>3 months) of beta-blockers or calcium channel blockers (CCB) (except verapamil) is allowed.
- 2) Unstable statin use <12 months. Stable use (>12 months) is allowed.
- 3) Use of full dose ritonavir, nelfinavir, clarithromycin, and other strong inhibitors of CYP3A4, as well as CYP3A4 inducers.
- 4) Continuous oral steroid use (equivalent to prednisone \geq 5 mg daily) within the last 3 months.

**MIneralocorticoid Receptor Antagonism for CardiovascuLar hEalth in HIV
The MIRACLE HIV Study**

- 5) Uncontrolled diabetes requiring insulin and/or HbA1c > 7.5%.
- 6) Creatinine (Cr) > 1.5 mg/dL or estimated GFR<60 mL/min/1.73m².
- 7) K > 5.5 mEq/L.
- 8) Hemoglobin < 10 g/dL.
- 9) Known liver disease or ALT >3x ULN.
- 10) History of congestive heart failure, stroke, myocardial infarction, or known coronary artery disease.
- 11) Pregnant, actively seeking pregnancy or breastfeeding. Women of childbearing age may be on a non-hormonal form of contraception.
- 12) Estrogen, progestin derivative, or other sex steroid use within last 3 months. Stable physiologic testosterone replacement (> 3 months) is acceptable.
- 13) Current bacterial or other infections.
- 14) Active substance abuse.
- 15) Significant radiation exposure over the course of the year prior to randomization (e.g., radiation therapy, PCI, catheter ablation of arrhythmia) within 12 months of randomization.
- 16) Previous reaction or contraindication to gadolinium.
- 17) Coronary artery luminal narrowing >70% on coronary CTA.

Source of subjects and recruitment methods:

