Upon confirmation of eligibility, subjects will be given the option through a formal consenting process to participate in the substudy prior to randomization. Participation in the main study will not be affected if subjects choose to decline participation in the substudy; however, subjects withdrawn from the main study will be withdrawn from the substudy.

If subjects do not qualify for the main study following completion of both screening visits, subjects will be given the option to participate in an optional blood sampling visit.

Treatment assignment and randomization:

During the Baseline Visit randomization will be done. Subjects will be randomized 1:1 to receive eplerenone PO 50mg daily or identical placebo for 12 months. The randomization list, stratified by gender, statin use, and presence of plaque will be generated by the biostatistician and kept by the research pharmacy. Daily dosing starts at 50 mg for the first week to avoid hypotension and will be increased to 50 mg twice daily at the 1 week safety visit. The study will be double-blinded. All subjects will receive lifestyle modification as described below.

Prior to randomization in all cases, the subject's primary care physician will be consulted regarding the appropriateness of the protocol including the lifestyle modification program with the subject's permission. Subjects are not eligible if they do not meet all of the enrollment criteria.

In the event that a subject wishes to withdraw from the study, the subject will be asked to return all unused study medication.

V. Study Procedures

Data Collection

Screening Visit 1 (to determine eligibility):

We will obtain:

- 1) Informed consent, history and physical, urine pregnancy test for females.
- 2) Blood for Cr, K, ALT, CBC, HbA1c, and HIV viral load.

Screening Visit 2 (to determine eligibility): Subjects will present after a 12 hr fast. If eligible from Screening Visit 1, we will obtain:

- 1) Urine pregnancy test for females as appropriate.
- 2) Coronary CTA for coronary plaque assessment. (This will not be performed if the subject has a previous reaction or contraindication to iodine-containing contrast media).
- 3) CT Abdomen for single slice screening at L4 for VAT determination.

Optional Blood Sampling Visit (For those who do not qualify after both screening visits): Subjects will present after an overnight 12 hr fast.

- 1) Fasting blood for markers of heart disease and inflammation

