Aim VI: In an exploratory analysis, subjects will be enrolled using a factorial sampling strategy into 4 analytic strata (low VAT/absence of plaque, low VAT/presence of plaque, high VAT/absence of plaque, high VAT/presence of plaque). Using this design, we will first analyze whether there are differences in markers of inflammation and heart disease by VAT status (main effects model comparing presence and absence of excess VAT) using student's t-test for variables that are normally distributed or Wilcoxon rank sum test for variables that are not normally distributed. Based on the exclusion criteria excess VAT is determined to be $>110\text{cm}^2$. After assessing for differences in VAT in the main effects model, we will examine the degree to which markers of inflammation and heart disease are related to coronary plaque in both the high and low VAT groups, and whether this relationship is stronger in the coronary plaque group as a result of increased VAT using ANOVA for variable that are normally distributed and Kruskal-Wallis Test for variables that are not normally distributed.

VII. Risks and Discomforts

Blood Drawing: The total blood drawn for subjects completing the study is equivalent to approximately 560 ml (over a period of 12 months). This quantity of blood drawing does not pose excessive risk to subjects. By comparison, the Red Cross allows a healthy adult to donate 1 pint of blood every 8 weeks, which is about 473 ml. Subjects with a hemoglobin < 10 mg/dL will be excluded from the study. There will be minimal risk and

Mineralocorticoid Receptor Antagonism for Cardiovascular Health in HIV The MIRACLE HIV Study

discomfort associated with blood drawing and IV placement. The risks of these procedures are minor bruising or bleeding at the site of the blood draw or IV catheter or feeling faint. Standard clean insertion techniques will be utilized to minimize risk of infection.

Intravenous Catheter Placement: There are minor risks and discomforts associated with having an intravenous line and with injection of contrast agent through the intravenous line, including the possibility of bleeding, pain, inflammation (redness and swelling), and leaking of contrast agent outside of the vein at the site of the IV. These problems usually self-resolve or only require minor treatments, such as application of an ice-pack or slight pressure for a few minutes.

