CT Abdomen: This study is obtained once during the screening process to evaluate for visceral adipose tissue area. The radiation risk associated with the single slice CT scan of the abdomen is approximately 0.55 mSv. This is equivalent to the amount of radiation an individual would normally get in 2 months from natural background sources from the earth and the sky. As with the other imaging studies, there may be incidental findings on the CT study. If any of these findings are clinically significant, the subjects will be withdrawn from the study and referred to the primary care physician for further evaluation.

Coronary CTA and Radiation: With the implementation of measures to limit radiation exposure, the total dose of the coronary CTA examination will be approximately 4 mSv, depending on the weight, gender and heart rate. The added radiation from the two CTA scans (screening and follow-up) will be 8 mSv. This is equivalent to the amount of radiation an individual would normally get in 2 years and 7 months from natural background sources from the earth and the sky. State-of-the-art dose reduction techniques at MGH allow the dose to be substantially lower than historically reported median coronary CTA doses. Iterative image reconstruction algorithms allow for further reductions in radiation dose. These techniques allow for up to a 50% reduction in radiation dose compared with previous generation protocols. Massachusetts General Hospital was the first hospital in New England to use the Siemens Definition Flash second-generation dual-source 128 or Siemens SOMATOM Force dual-source 196 detector-row CT, an advanced cardiac-capable CT scanner which allows ultra-fast cardiac imaging at the lowest possible radiation doses potentially equivalent to or less than a chest CT scan. HIV patients may have clinically significant subclinical CAD. We will assess the first coronary CTA for this condition. Any subject with evidence of severe coronary artery stenosis, defined as $\geq 50\%$ stenosis in the left main coronary artery or $> 70\%$ stenosis in the other major coronary arteries will be withdrawn from the study prior to further evaluative imaging and procedures and prior to randomization to study drug. Subjects with evidence of clinically significant atherosclerosis will be referred to a cardiologist for appropriate evaluation and treatment.

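### Aim VI's four VAT-by-plaque groups cannot be filled as planned from the only stated source, subjects who fail after both screening visits

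*Combined protocol and SAP*

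**What the plan says.** **Source of subjects.** In II. Specific Aims, Aim VI stands under the heading "Optional Study for those who do not qualify following both screen visits". IV. Subject Enrollment says: "If subjects do not qualify for the main study following completion of both screening visits, subjects will be given the option to participate". What they are offered is one further visit for a blood draw. VII. Risks and Discomforts and VIII. Potential Benefits describe that visit in the same way.

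**Analysis.** VI. Biostatistical Analysis says that for Aim VI "subjects will be enrolled using a factorial sampling strategy into 4 analytic strata". It first compares inflammatory and cardiac markers between high and low VAT by t-test or Wilcoxon test. It then asks how the markers relate to plaque within each VAT group, and whether that relation is stronger when VAT is raised, by ANOVA or Kruskal-Wallis. The VAT cut-off of 110 cm² is taken from the trial's eligibility criteria. No sample size or cell size is given for this aim.

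**Main-trial eligibility.** III. Subject Selection requires VAT above 110 cm². It does not require plaque, and it excludes "Coronary artery luminal narrowing >70% on coronary CTA". IV. Subject Enrollment adds: "The randomization list, stratified by gender, statin use, and presence of plaque will be generated by the biostatistician". Sections V and VI repeat this stratification.

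**Screening order.** For Screening Visit 2, V. Study Procedures says: "If eligible from Screening Visit 1, we will obtain", followed by a pregnancy test where relevant, coronary CTA and a single-slice abdominal CT for VAT.

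**Severe stenosis.** VII. Risks and Discomforts (Coronary CTA and Radiation) defines it as at least 50% in the left main or more than 70% in another major coronary artery, and says such subjects "will be withdrawn from the study prior to further evaluative imaging and procedures and prior to randomization to study drug".

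**The concern.** Aim VI divides people by the same VAT threshold that decides entry to the main trial, yet its blood visit is offered only to people who failed to enter. Subjects who fail at Screening Visit 1 leave before CT and CTA, so those who fail after both visits are mostly people with low VAT. The plan nevertheless needs two high-VAT groups out of four.

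At stake are the hypothesised gradient across the four groups and the question whether VAT strengthens the relation between plaque and inflammation. Volunteers would give about 48 ml of blood at the optional visit for a comparison that the stated sampling cannot deliver.

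**Working it through.** The plan gives no figure for Aim VI to reproduce, so the check is one of logic.

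**Step 1. Apply the imaging criteria to each combination.** The inputs are VAT above 110 cm² for entry, no plaque requirement (both III), and exclusion for severe stenosis (III and VII).

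| VAT | CTA result | Main trial | Available to Aim VI as a non-qualifier |
|---|---|---|---|
| ≤110 cm² | no plaque | fails | yes |
| ≤110 cm² | plaque, not severe | fails | yes |
| ≤110 cm² | severe stenosis | fails | yes, if withdrawal allows the visit |
| >110 cm² | no plaque | qualifies | no |
| >110 cm² | plaque, not severe | qualifies | no |
| >110 cm² | severe stenosis | fails | yes, if withdrawal allows the visit |

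On these criteria both low-VAT groups can be filled. High VAT without plaque has no members. High VAT with plaque consists of severe stenosis.

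**Step 2. What can be estimated.** Let m be a cell mean, with L or H for VAT and N or P for no plaque or plaque. The question whether VAT modifies the plaque relation is the contrast (m_HP − m_HN) − (m_LP − m_LN). In a 2×2 model with columns intercept, VAT, plaque and VAT×plaque, the rows are:

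- LN: 1, 0, 0, 0
- LP: 1, 0, 1, 0
- HN: 1, 1, 0, 0
- HP: 1, 1, 1, 1

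With all four rows the rank is 4. Without HN it is 3: the VAT and VAT×plaque columns are then both 0, 0, 1 and cannot be separated. If subjects with severe stenosis are also barred from the optional visit, only LN and LP remain and the rank is 2, with no VAT comparison at all.

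**Step 3. The planned VAT test.** The t-test or Wilcoxon test is unadjusted. On this sampling it sets a high-VAT group made up essentially of severe stenosis against a low-VAT group that mixes no plaque, non-severe plaque and some severe stenosis.

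**Step 4. The pool.** III allows up to 160 consents and the main trial enrols 80. At most 160 − 80 = 80 consented subjects remain, and those who fail Screening Visit 1 never reach imaging. The documents give no split by VAT or plaque, so cell sizes cannot be computed.

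**Step 5. The alternative reading.** II. Specific Aims describes the population as having subclinical atherosclerosis. If plaque were required for entry, subjects with high VAT and no plaque would fail and could fill that cell. High VAT with plaque would still be essentially severe stenosis, so the plaque contrast within high VAT would remain confounded. The inclusion list in III and the stratification by plaque do not support this reading.

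**Step 6. With main-trial participants added.** They have VAT above 110 cm², with or without plaque. All four cells can then be filled and the rank is 4 of 4.

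**The case against.** The strongest reply is that the Aim VI analysis text does not itself confine the analysis to non-qualifiers. Main-trial participants are the natural high-VAT groups. They are stratified by plaque and already give fasting, pre-treatment blood for inflammatory and cardiac markers at the Bionutrition Visit. The optional visit may have been meant only to add the missing low-VAT groups. This is plausible and the documents do not rule it out. But no text says it, the analysis section speaks of enrolling into the strata, and the Aim VI heading and every description of its blood visit refer to non-qualifiers.

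A reader might also infer that one cell is strictly empty and another holds nothing but severe stenosis. The documents do not support this. Subjects can leave late for reasons unrelated to VAT or plaque: a repeat pregnancy test, the primary care consultation before randomisation, or an incidental CT finding ("If any of these findings are clinically significant, the subjects will be withdrawn from the study and referred to the primary care physician"). Such subjects would be few and selected, so they cannot supply a planned stratum, but they rule out the absolute wording.

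Nor does it follow that the VAT effect is wholly confounded or cannot be estimated. Everyone with low VAT fails screening whatever the CTA shows, so the low-VAT plaque group can also contain severe stenosis, and VAT groups could be compared within it. With three cells filled, an additive VAT-plus-plaque model is still estimable. What stands is narrower: the interaction is lost, and the planned VAT test makes no allowance for stenosis.

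Finally, Aim VI is labelled exploratory and carries no power claim. That limits the importance of the point but does not remove it.

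**Conclusion.** The point holds in this form. Taken as written, the only stated source supplies essentially no subjects with high VAT and no plaque and, for high VAT with plaque, essentially only severe stenosis. The interaction and the four-group gradient cannot then be estimated (rank 3 of 4), and the unadjusted VAT comparison is heavily confounded. If the withdrawal rule in VII also covers the optional visit, the remaining high-VAT cell may hold nobody (rank 2).

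This rests on two assumptions: that plaque is not an entry requirement, as the inclusion list and stratification indicate, and that late exits for other reasons are few. The documents give no counts for the second. The finding does not touch randomisation or Aims I to V.

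**What to change.** 1. In Aim VI and the enrolment text, state that the high-VAT strata come from main-trial participants, using their pre-treatment fasting Bionutrition Visit blood, and that the optional visit supplies the low-VAT strata.
2. Flag subjects with severe stenosis, or analyse them separately, in both VAT groups.
3. Reconcile II. Specific Aims with III. Subject Selection on whether plaque is required for entry.
4. Reconcile IV. Subject Enrollment with VII. Risks and Discomforts on whether subjects withdrawn for severe stenosis may attend the optional visit. III and VII also need to agree on the definition, since only VII has a left main threshold.

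The cost is protocol wording, consent wording where needed, and any assays not already planned on the main-trial samples. One limitation should be recorded: both visits specify a 12-hour fast, but only the Bionutrition Visit specifies an ad lib diet, so a diet difference between the two sources is possible.
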